8.6.1 Biochemistry

Blood samples for biochemistry will include the assessment of parameters listed in [Table 3](#), according to the times indicated in [Table 1](#) and [Table 2](#).

Any unscheduled test (indication and results) will be recorded on the dedicated page in the eCRF.

8.6.2 Hematology

Blood samples for hematology will include the assessment of parameters listed in [Table 3](#), according to the times indicated in [Table 1](#) and [Table 2](#).

Any unscheduled test (indication and results) will be recorded on the dedicated page in the eCRF.

8.6.3 Urinalysis

Fresh urine samples will be collected and will include the assessment of parameters listed in [Table 3](#), according to the times indicated in [Table 1](#) and [Table 2](#). Any abnormalities detected on dipstick at Screening (Visit 1), Pre-harvest (Visit 2, Assessment A) and Baseline (Visit 3, Assessment C) will require repeat dipstick and microscopic examinations.

Microscopic tests will be performed, if indicated, but results will not be collected in the eCRF. If, in the opinion of the Investigator, there are any clinically significant abnormalities under microscopy, they will be recorded as an AE in the eCRF.

8.6.4 Pregnancy Test

Serum HCG pregnancy tests will be performed on all females of child-bearing potential at times indicated in [Table 1](#).

8.6.5 HIV-1, HepB, ParvoB19

These tests will be performed at baseline to determine eligibility.

8.7 Blood Volume

The total volume of blood drawn for each assessment visit is estimated to be between 15 to 90 ml (2 to 6 tablespoons) for each subject.

8.8 Pharmacokinetic Evaluations of Busulfan

Blood samples to determine plasma Busulfan concentrations will be drawn after the first and second doses of Busulfan to calculate the AUC at times indicated in [Table 1](#).

9 STATISTICAL METHODS

9.1 Background

The primary objective of this clinical study is to further explore the safety and efficacy of OTL-101, an autologous, genetically modified CD34+ HSC based gene therapy for the treatment of ADA-SCID. The study will also be supportive of the analytical CMC comparability studies between fresh and cryopreserved OTL-101 formulations. The clinical outcomes (good predictors of survival and event free survival): RBC ADA >0 Units, absolute CD3+ T-cell counts $\geq 200/\text{mm}^3$, and peripheral blood samples positive for vector sequences by qPCR($>1/10,000$ cells) will be assessed as part of an interim analysis following completion of the 6 month follow-up visit.

9.2 Design Considerations and Data

This is a prospective, non-randomized, single-cohort, longitudinal, single-center, clinical study aimed to further evaluate the safety and efficacy of OTL-101.

Descriptive results will be presented for the study cohort.

9.3 Study Endpoints

The efficacy, including exploratory endpoints, are detailed in [Section 7.1](#) and the safety endpoints are detailed in [Section 8.1](#).

9.3.1 Primary Efficacy Endpoints

The primary efficacy endpoints for this study include treatment success at 6 months post OTL-101 infusion, and overall survival and event-free survival at 12 months post OTL-101 infusion.

Treatment success at 6 months post OTL-101 infusion, will be performed in support of CMC assessing comparability between cryopreserved and fresh formulations. Evaluation of the success of therapy will be based on the following parameters and their thresholds:

- a) Erythrocyte ADA enzyme activity above baseline/pre-treatment level (>0 Units),
- b) Absolute CD3+ T-cell counts $\geq 200/\text{mm}^3$, and
- c) Peripheral blood samples positive for vector sequences by qPCR($\geq 1/10,000$ cells).

Treatment will be deemed successful in subjects meeting all three above thresholds. These subjects will be designated as “responders”. Those subjects failing to meet at least one of the above thresholds will be considered to be “non-responders.”

Overall Survival is defined as the time-to death from the OTL-101 infusion if death occurred, or to the date of the last evaluation if death did not occur. If no death occurred, the subject’s data will be considered censored at the last evaluation.

Event Free Survival is defined as the time-to event from the OTL-101 infusion if an event occurred, or to the date of the last evaluation without an event if no event occurred. If no event occurred, the subject’s data will be considered censored at the last evaluation. Event is defined as any of the following:

- Death
- Returning to PEG-ADA ERT
- Need of rescue HSCT

9.3.2 Secondary Efficacy

The secondary efficacy endpoints will be assessed at 12 and 24 months post OTL-101 administration and include:

- Overall survival and event free survival 24 months post OTL-101 infusion,
- Use of immunoglobulin replacement therapies prior to and after OTL-101 infusion,
- Assessment of performance outcomes and quality of life measured by the Karnofsky/Lansky scale and questions relevant to general well-being, school attendance and ability to practice sports, respectively,
- Rate of severe infections/opportunistic infectious episodes, defined as infections requiring hospitalization or prolonging hospitalization and/or documented infections by opportunistic pathogens (e.g. interstitial pneumonia, intractable diarrhoea),
- Response to tetanus vaccination,
- Immune reconstitution: T and B cell reconstitution.

All summaries of secondary endpoints will be descriptive.

9.3.3 Exploratory Efficacy Endpoints

The following laboratory correlates of efficacy will be used to assess the level of gene correction, engraftment and immune reconstitution:

- Quantification of clonal diversity of vector integrants.
- TREC and FACS for TCR V-beta family use.
- Percentage gene marking in peripheral blood cells.
- Adenosine deaminase enzyme activity in erythrocytes.
- Total adenine nucleotides in erythrocytes.
- Vector integration analysis.
- Immune reconstitution
 - Absolute Lymphocyte Count.
 - Absolute numbers of T, B, NK lymphocytes in peripheral blood.
 - T lymphocyte proliferative responses to mitogen (PHA) and to antigens (tetanus toxoid after vaccination)
 - Serum immunoglobulin levels (IgG, IgA and IgM).

All summaries of exploratory endpoints will be descriptive.

9.3.4 Safety Endpoints

Safety endpoints in this study are AEs, including SAEs, with severity graded by Common terminology criteria for adverse events (CTCAE) criteria, including relation to treatment. Special attention will be paid to the following AE types:

1. Clinical toxicities
2. Exposure to RCL

3. Development of monoclonal expansion or leukoproliferative complications from vector insertional effects.

9.4 Sample Size Considerations

Due to the ultra-orphan nature of this indication, the sample size for this study is based on practical considerations. Specifically, the number of ADA-SCID patients expected to meet eligibility criteria yearly is around four to five. With a planned enrollment of three to six subjects per year, the sample size (N=10) for this study is considered reasonable.

It should be noted that the sample size will provide precision of 15% for 100% success (survival) at any particular time point. Precision is here defined as the half-width of the two-sided 95% CI using the Exact Binomial computations.

Ten subjects receiving OTL-101 will participate in this study.

Although all subjects will be evaluable for the first analysis at 6 months post OTL-101 infusion, the first five subjects will be reviewed to monitor the outcome of the study treatment. Sample size considerations for the first analysis of five subjects completing the 6-month follow-up assessment is based on realistic enrollment for this orphan indication. Experts in the field of HSCT and gene therapy use RBC ADA enzyme activity >0 U, absolute CD3+ T-cell counts $\geq 200/\text{mm}^3$, and peripheral blood samples positive for vector sequences by qPCR ($>1/10,000$ cells) as predictors of survival and event free survival and ultimately the success of the OTL-101 treatment. These parameters achieve plateau between 3 and 4 months post-intervention, therefore, a 6-month data cut for this interim analysis should be indicative of the final study outcomes.

9.5 Analysis Populations

9.5.1 Efficacy Population

The efficacy population will be a modified intent-to-treat population including all subjects treated with OTL-101 within this protocol.

9.5.2 Safety Population

The safety population will consist of all subjects treated with OTL-101 within this protocol.

9.5.3 Pharmacokinetic Population

The PK population will include all subjects who have received at least one dose of Busulfan and for whom there are sufficient plasma samples to allow reliable determination of PK profile. Subjects' evaluability will be determined by the Investigator.

9.6 Statistical Methods

9.6.1 Overview

Full statistical methods will be detailed in the statistical analysis plan (SAP). The data will be summarized in tables displaying the mean, standard deviation, median, minimum, maximum and number of subjects for continuous data (e.g. age, weight) or in tables displaying count and percentage for categorical data (e.g. gender, previous treatment). Data will be presented by visit, if applicable.

All statistical analyses will be performed using Statistical Analysis System (SAS)® Version 9.4. or higher.

Statistical analyses will be performed, and their outcomes presented, in three stages:

1. The first (interim) analysis will compare the success/failure data 6-months post OTL-101 infusion. The success/failure of the OTL-101 cryopreserved formulation will be defined by the three criteria listed in the primary objectives ([Section 2.2.1](#)). This data will be compared with available data from the ongoing UCLA Phase I/II study using the OTL-101 fresh formulation. This will support the CMC comparability data between OTL-101 cryopreserved and fresh formulations. Secondary and exploratory endpoints will also be described.
2. The second (primary) analysis will determine the 12 month overall survival and event free survival for all subjects. Secondary and exploratory endpoints, as well as baseline characteristics, subject disposition, and safety data will also be described.
3. The third (final) analysis will be performed to determine the overall survival and event free survival for all subjects 24 months post OTL-101 infusion. Secondary and exploratory endpoints, as well as baseline characteristics, subject disposition, safety and Busulfan PK data will also be described.

This study is not designed to be powered to demonstrate statistical significance; therefore, no correction for overall Type I Error will be performed.

9.6.2 Subject Disposition

Subject disposition will be tabulated; the number of enrolled, exposed, prematurely terminated, ongoing and completed subjects will be summarized. A list of dropouts will be prepared including treatment received, reason for discontinuation, and time of discontinuation.

9.6.3 Baseline Characteristics

The following information collected at baseline will be presented:

- Demographics (Age, Gender, etc.),
- Method of diagnosis,
- Previous HSCT including: date, transplant cells, donor type and outcome,
- Previous PEG-ADA ERT (and duration of treatment),
- Previous or current immunoglobulin therapy,
- Listing of relevant medical history, including infections.

9.6.4 Efficacy Analyses

The primary efficacy endpoints will be summarized as follows:

Responder Analysis

The proportion of responders in this study will be summarized and compared with the proportion of responders in the Phase I/II ongoing studies using the fresh formulation.

Overall and Event Free Survival

Overall and event free survival will be summarized using:

- Proportion of patients who survived at each specified analysis timepoint, with the exact binomial 95% confidence interval.
- Kaplan-Meier survival curve of time to death/event.

All efficacy summaries will be descriptive, there will be no formal statistical comparisons.

9.6.5 Safety Analyses

All AEs will be coded according to the current Medical Dictionary for Regulatory Activities (MedDRA) version and will be classified by MedDRA preferred term and system organ class. AE listings will be presented by subject, system organ class and preferred term. Incidence of treatment emergent AEs (TEAE) and SAEs will be tabulated by system organ class and preferred term. In addition, summary tables will be presented by maximum severity, relationship to treatment and TEAEs associated with premature withdrawal from the study.

A TEAE is defined as any AE that occurs during the active phase of the study if:

- it was not present prior to receiving the OTL-101 infusion, or
- it was present prior to receiving the OTL-101 infusion but the intensity increased during the active phase of the study, or
- it was present prior to receiving the OTL-101 infusion, the intensity is the same but the drug relationship became related during the active phase of the study.

Summary statistics (mean, median, SD and range as appropriate) will be presented for vital signs, ECG parameters and clinical laboratory tests at each assessment along with change from baseline. For laboratory data, abnormal values will be flagged in the data listings. Shift tables will be presented of the number and percentage of subjects with low, normal or high values and normal or abnormal examinations at each visit and overall.

9.7 Pharmacokinetic Analysis

Pharmacokinetic blood samples will be collected before each Busulfan dose is administered, at the end of Busulfan infusion, +1, 2, 4, 8, and 13 hours post-infusion (+/- 15 minutes).

The following Busulfan PK parameters will be summarized. In addition, graphical presentation of average concentration (using original and log scale) will be presented over time.

C_{\max}	Maximum plasma concentration achieved
T_{\max}	Time to C_{\max} (peak exposure)
AUC_{0-t}	The area under the plasma concentration-time curve up to the last quantifiable concentration (LOQ; limit of quantitation) from time of administration ($t=0$) up to the selected interval after the injection, calculated by the linear trapezoidal method
AUC_{0-13}	The area under the plasma concentration-time curve during the first 13 hours post injection, calculated by the linear trapezoidal method
$AUC_{0-\infty}$	The area under the plasma concentration-time curve extrapolated to infinity, calculated as: $AUC_{0-\infty} = AUC_{0-t} + Clast/\lambda_z$, where $Clast$ is the last measurable ($>LOQ$) concentration.
λ_z	Elimination rate constant determined by linear regression of the terminal points of the ln-linear plasma concentration-time curve
$t_{1/2}$	Terminal elimination half-life, defined as $0.693/\lambda_z$

10 DIRECT ACCESS TO SOURCE DATA AND DOCUMENTS

The Investigator must maintain the primary records (i.e. source documents) of each subject's data at all times. The Investigator will maintain a confidential subject identification list that allows the unambiguous identification of each subject. All study related documents must be kept until notified by the Sponsor.

The medical experts, study monitors, auditors, and health authority inspectors (or their agents) will be given direct access to source data and documentation (e.g. medical charts/records, laboratory test results, printouts, videotapes) for source data verification, provided that subject confidentiality is maintained in accordance with local requirements.

Authorized personnel from external CAs, Clinical Research Organization (CROs) and Quality Assurance personnel authorized by the Sponsor may carry out inspections and audits. The purpose of an audit is to ensure that ethical, regulatory and quality requirements are fulfilled in all studies performed by the Sponsor. Auditors and inspectors must have direct access to the study documents and site facilities as specified in [Section 11.5](#), and to any other locations used for the purposes of the study in question (e.g. laboratories).

In the event of the site being notified directly of a regulatory inspection, the Investigator must notify the Sponsor's representative as soon as possible, to assist with preparations for the inspection.

11 QUALITY CONTROL AND QUALITY ASSURANCE

11.1 Protocol Amendments

11.1.1 Protocol Amendments

No changes from the final approved (signed) protocol will be initiated without the prior written approval or favorable opinion of a written amendment by the IEC/IRB and CAs, except when this is necessary to eliminate immediate safety concerns to the subjects or when the change involves only logistics or administration. The principal Investigator and the Sponsor will sign the protocol amendment.

In the event that an amendment to this protocol is required, it will be classified into one of the following three categories:

Administrational changes are those that are not considered ‘substantial’ (e.g. administrative changes) and as such are not required to be notified to the IEC/IRB or CAs but are contained in the protocol under a subsequent notification of a substantial amendment.

Substantial Amendments are those considered ‘substantial’ to the conduct of the clinical study where they are likely to have a significant impact on:

- the safety or physical or mental integrity of the subjects,
- the scientific value of the study,
- the conduct or management of the study, or
- the quality or safety of the protocol treatment used in the study.

Substantial amendments must be notified to the IEC/IRB and CAs. Prior to implementation, documented approval must be received from the IEC/IRB and either explicit approval or no raise of grounds of non-acceptance during the regulatory review period (country specific) must be received from the relevant CAs.

Urgent Amendments are those that require urgent safety measures to protect the study subjects from immediate hazard and as such may be implemented immediately by the Sponsor with subsequent IEC/IRB and CAs notification, forthwith.

11.1.2 Protocol Deviations, Violations, and Exceptions

A protocol deviation concerns non-compliance with protocol-specific study procedures or schedules that do not involve inclusion/exclusion criteria, primary objective evaluation criteria, and/or GCP guidelines. Such deviations are considered to be minor and do not impact the study.

A protocol violation is any clinically significant divergence from the protocol, i.e. non-compliance by the subject, the Investigator, or the Sponsor with protocol-specific inclusion/exclusion criteria, primary objective evaluation criteria, and/or GCP guidelines. Protocol violations will be identified and recorded, by study center personnel, in the eCRF.

As a matter of policy, the Sponsor will not grant any exemptions from the protocol-specific entry criteria in order to allow subjects to enter a study. If, under extraordinary circumstances, such an action is considered ethically, medically and scientifically justified for a particular subject, prior approval from the Sponsor and the responsible IEC/IRB is required before the subject will be allowed to enter the study. If staff at an investigational center learn that a subject who did not meet the protocol eligibility criteria was entered in a study (a protocol violation), they must inform the Sponsor immediately. Such subjects will be withdrawn from the study,

except in exceptional cases following review and written approval by the Sponsor and the responsible IEC/IRB.

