A subject may discontinue participation in the study at any time for any reason (for example lack of efficacy, withdrawal of consent, AE). The Investigator and/or Sponsor can withdraw a subject from the study at any time for any reason (for example protocol violation or deviation as defined in [Section 4.3](#), non-compliance with the protocol, or AE).

The Investigator should assess the ongoing risk-benefit ratio of each subject during their participation in the study, in consideration of any AEs and the potential benefits of continued treatment with OTL-101 or any alternative therapies.

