7.1 Efficacy Population

The efficacy population will be a modified intent-to-treat population including all subjects treated with OTL-101 within this protocol.

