7.2 Safety Population

The safety population will consist of all subjects treated with OTL-101 within this protocol.

8 Statistical Methods

In general, continuous variables will be summarized using the mean, standard deviation, minimum, median, maximum and number of subjects. Categorical variables will be summarized using number of subjects and percentages.

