8.3.1.2 Overall Survival at 12 Months

Overall survival will be evaluated using the time in months from transplant to either the subject’s death or their last evaluation calculated as:

$$12 * (\text{date of death/last evaluation} - \text{date of transplant}) / 365.25.$$

The number (%) of subjects who were still alive at 12 months post-transplant will be summarized. For the purpose of this analysis, any subject who withdrew from the study prior to 12 months, who was known to be alive at the last evaluation, will have a status of “unknown”. The proportion and exact 95% confidence interval (CI) for survivors at 12 months post-transplant will be calculated.

Overall survival will also be represented using a Kaplan-Meier curve for time to death. For the purpose of this analysis, any subject who withdrew from the study prior to 12 months and was known to be alive at the last evaluation will be censored at the date of their last evaluation. If appropriate, the proportion alive at 12 months and the associated 95% CI will be estimated from the Kaplan-Meier curve along with the median survival time (and interquartile range), if they can be estimated from the data.

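### Protocol 11.1.2 withdraws subjects found ineligible after entry without exempting those already infused, so a treated child can stay in the analysis set while losing scheduled endpoint and vector-safety follow-up

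*Protocol*

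**What the plan says.** **The withdrawal rule.** Protocol 11.1.2 deals with a subject who was entered and later turns out not to have met the entry criteria. Once the sponsor has been told, "Such subjects will be withdrawn from the study", "except in exceptional cases following review and written approval by the Sponsor and the responsible IEC/IRB". The section does not separate subjects who have received OTL-101 from those who have not, and it gives no criteria for an exceptional case.

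**A second power.** Protocol 3.6.1 adds: "The Investigator and/or Sponsor can withdraw a subject from the study at any time for any reason". It gives a protocol violation as one example.

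**The analysis sets.** Protocol 9.5.1 defines the efficacy set as a "modified intent-to-treat population including all subjects treated with OTL-101 within this protocol", and SAP 7.1 repeats this. SAP 7.2 reads: "The safety population will consist of all subjects treated with OTL-101 within this protocol". Late-found ineligibility therefore removes nobody from either set.

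**How withdrawals are counted.** SAP 8.3.1.2 gives a status of 'unknown' to "any subject who withdrew from the study prior to 12 months, who was known to be alive at the last evaluation", and censors that subject in the Kaplan-Meier analysis. SAP 8.3.1.3 applies the same handling to event-free survival, and SAP 8.3.2.1 applies it at 24 months. SAP 8.3.1.2 does not say whether an 'unknown' subject counts in the denominator of the exact confidence interval.

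**The concern.** Ineligibility is a reason not to give a product. Once the product has been given, it is a weak reason to stop observing the child. Section 11.1.2 does not separate the two. Applied as worded to an infused child, it ends data collection on a subject whom the analysis plan still counts.

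Four things are at stake:
- **12- and 24-month overall and event-free survival.** A child withdrawn alive and event-free before the time point has no outcome there.
- **The Month 6 responder endpoint**, if withdrawal comes earlier. The fallback in SAP 8.3.1.1 for missing Month 6 values uses the first later assessment, and a withdrawn child has none in the study.
- **Scheduled vector safety.** Protocol Table 2 plans replication-competent lentivirus assays at Months 3, 6, 12 and 24, and vector integration analysis at Months 3, 6, 12, 18 and 24. Both bear on the study-level halting rules in Protocol 3.6.1 (items 3 and 4).
- **Who stays.** Retention depends on a case-by-case exception without stated criteria, in a study that Protocol 3.3 describes as unblinded.

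The rule is also out of line with two other places in the protocol. If enrolment is halted (3.6.1), endpoint evaluation of subjects already infused goes on. A subject who restarts enzyme replacement (6.2.1.1) is kept in follow-up.

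**Working it through.** **Can the rule reach an infused child?** Entry comes before infusion (Protocol 5.1.1). Protocol 3.5 puts total participation at up to 2 years 4 months, of which 2 years follow infusion: 24/28 = 86%. Source verification by the monitor runs through the study (3.9, 11.4), so a breach can surface after infusion. That the rule then applies is inferred from its unrestricted wording; the text does not say so expressly.

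**What follow-up remains?**
- A final evaluation at withdrawal (4.3).
- An early termination visit, encouraged but not required (4.4, 5.1.8). It includes the lentivirus assay and serum banking, and leukaemia monitoring if triggered. It does not include vector integration analysis (5.1.8, Table 2).
- Adverse events followed until resolved or stable (8.2.2), and reporting of suspected related events after the study (8.2.3).
- An invitation to a registry under a separate protocol and separate consent (5.1.8, 5.1.9).

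None of these produces a scheduled Month 12 or Month 24 survival or event-free survival assessment in this study.

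**The plan's own precision figure.** Protocol 9.4 gives a precision of 15% at 100% success with N = 10, as the half-width of the two-sided exact 95% interval.
- For x = n, the lower limit is 0.025^(1/n) and the upper limit is 100%.
- For n = 10: 0.025^(1/10) = 69.2%. The half-width is (100 − 69.2)/2 = 15.4%, which reproduces the stated 15%.

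**One or two infused children withdrawn before 12 months.** These are illustrative counts, and every other child is taken to be alive. For x < n the limits are the 2.5% quantile of Beta(x, n − x + 1) and the 97.5% quantile of Beta(x + 1, n − x).

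| Withdrawn | 'Unknown' dropped | Half-width | 'Unknown' kept, counted as not alive | Half-width |
|---|---|---|---|---|
| 0 | 10/10: 69.2–100% | 15.4% | 10/10: 69.2–100% | 15.4% |
| 1 | 9/9: 66.4–100% | 16.8% | 9/10: 55.5–99.7% | 22.1% |
| 2 | 8/8: 63.1–100% | 18.5% | 8/10: 44.4–97.5% | 26.5% |

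**Worst case.** Suppose the one withdrawn child would later have had an event.
- With full follow-up: 9/10 = 90% (55.5–99.7%).
- Withdrawn, 'unknown' dropped: 9/9 = 100% (66.4–100%).
- Withdrawn, 'unknown' counted as a failure: 9/10, the same as with full follow-up.
- Kaplan-Meier: the child is censored. If nobody else has an event, the curve never steps down and the estimate is 100%.

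**How likely is one such child?** The documents give no rate. Let p be the assumed chance, per infused subject, of ineligibility being found after infusion. The chance of at least one in 10 is 1 − (1 − p)^10:
- p = 1%: 9.6%
- p = 2%: 18.3%
- p = 5%: 40.1%
- p = 10%: 65.1%

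This range shows sensitivity to p and is not an estimate.

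**The case against.** **Late detection is a residual case.** Eligibility is checked at screening, and further tests follow before harvest and before conditioning. Manufacture and release take 30–45 days, and a monitor checks source records. Most breaches should surface before infusion, and the exception clause could cover the rest. This stands, and it limits how often the rule would bite. It does not give the rule a default that suits a treated child.

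**A reader might infer that follow-up is lost at the sponsor's discretion.** Section 11.1.2 does not support that. Withdrawal there is the default and not a choice, and an exception needs the ethics committee as well as the sponsor. That independent approval lowers the risk that retention follows outcome, and the documents give no evidence that it would. The sponsor can act alone only under the general power in 3.6.1, which is a separate provision.

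**A reader might infer that safety monitoring stops.** It is curtailed. The remaining elements are real, and an early termination visit does include a lentivirus assay. What ends is the scheduled in-study series.

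**The 90% to 100% shift stacks assumptions.** It needs a late-found ineligible child, a later event in that same child, and, for the simple proportion, an 'unknown' dropped from the denominator. This is correct, so the shift is a worst case. The Kaplan-Meier estimate needs only the first two, provided no other child has an event.

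**Loss unrelated to outcome costs precision and does not bias, and the study is descriptive.** This is fair where the breach and the exception decision are both unrelated to prognosis. The precision loss remains, and the exact interval is the plan's own measure of what 10 subjects can show.

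**Conclusion.** The point holds as a gap in the withdrawal rule. As worded, Protocol 11.1.2 would keep an infused, ineligible child in both analysis populations while ending the scheduled assessments that those populations need. The remaining follow-up does not replace the Month 12 and Month 24 endpoints or the integration series.

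The size is conditional. For one such child in 10 with all alive, the half-width moves from 15.4% to 16.8% or 22.1%. The gap between those two figures comes entirely from the undefined handling of 'unknown'. The rise from 90% to 100% is the extreme scenario and should not be read as an expected effect. All of this rests on an assumed count, and on reading the rule's silence about infused subjects as including them.

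A change is worth making because each treated subject is a tenth of the data and the remedy is small. The documents do not show that any subject has been lost this way, or that retention would be chosen by outcome.

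**What to change.** 1. **Protocol 11.1.2:** limit withdrawal for ineligibility to subjects who have not yet received OTL-101. State that infused subjects found ineligible stay, subject to consent, in scheduled follow-up to Month 24 and in both analysis populations, with the violation reported.
2. **Protocol 3.6.1:** align the general withdrawal power, which names protocol violation, so that it does not reopen the same route for infused subjects.
3. **SAP 8.3.1.2** (and so 8.3.1.3 and 8.3.2.1): state how 'unknown' enters the denominator of the exact interval. Reporting both versions would show the range.
4. **Optional:** a sensitivity analysis excluding infused subjects who were ineligible.

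**Cost.** A short protocol text change, which may need ethics committee and authority review under Protocol 11.1.1 and could be combined with the next amendment, plus a short SAP edit. The visits are already planned. Withdrawal of Month 6 non-responders is a separate rule with a different trigger, and this change does not alter it.
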